9.5.5.2. Hepatic Safety

If a study patient experiences elevated alanine aminotransferase (ALT) \geq 3× upper limit of normal (ULN), alkaline phosphatase (ALP) \geq 2× ULN, or elevated total bilirubin (TBL) \geq 2× ULN, liver tests (Appendix 4) should be repeated within 3 to 5 days including ALT, aspartate aminotransferase, ALP, TBL, direct bilirubin, gamma-glutamyl transferase, and creatinine kinase to confirm the abnormality and to determine if it is increasing or decreasing. If the abnormality persists or worsens, clinical and laboratory monitoring should be initiated by the investigator based on consultation with the Lilly CP or CRP. Monitoring should continue until levels normalize and/or are returning to approximate baseline levels.

Additional safety data should be collected if 1 or more of the following conditions occur:

- elevation of serum ALT to >5× ULN on 2 or more consecutive blood tests
- elevated serum TBL to $\ge 2 \times$ ULN (except for cases of known Gilbert's syndrome)
- elevation of serum ALP to $\ge 2 \times$ ULN on 2 or more consecutive blood tests
- patient discontinued from treatment due to a hepatic event or abnormality of liver tests
- hepatic event considered to be an SAE.

9.6. Pharmacokinetics

At the visits and times specified in the Schedule of Activities (see Section 2), venous blood samples of approximately 4 mL each will be collected to determine the plasma concentrations of

glucagon. Three samples may be collected per patient at additional time points during the study if warranted and agreed upon between both the investigator and sponsor. Instructions for the collection and handling of blood samples will be provided by the sponsor. The actual date and time (24-hour clock) of each sampling will be recorded.

9.6.1. Bioanalysis

Samples will be analyzed at a laboratory approved by the sponsor and stored at a facility designated by the sponsor.

Concentrations of glucagon will be assayed using a validated liquid chromatography with tandem mass spectrometry method.

Bioanalytical samples collected to measure investigational product concentrations will be retained for a maximum of 1 year following last patient visit for the study.

9.7. Pharmacodynamics

At times specified in the Schedule of Activities (see Section 2), venous blood samples will be collected and used to determine PG concentrations.

The samples will be stored for up to a maximum of 1 year after last patient visit for the study at a facility selected by the sponsor.

9.7.1. Immunogenicity Assessments

At the visits and times specified in the Schedule of Activities (Section 2), venous blood samples will be collected to determine antibody production against glucagon. To interpret the results of immunogenicity, a venous blood sample may be collected at the same time points to determine the concentrations of glucagon. All samples for immunogenicity should be taken predose when applicable.

In the event of drug hypersensitivity reactions (immediate or non-immediate), additional immunogenicity samples will be collected as close to the onset of the event as possible, at the resolution of the event, and 30 days following the event. A PK sample may be collected at these same time points(s) if warranted and agreed upon between both the investigator and sponsor.

Treatment-emergent antidrug antibodies (TE ADA) are defined in Section 10.3.6. If the immunogenicity titer at the last scheduled assessment or discontinuation visit meets the definition of treatment emergent, then, at the discretion of the sponsor, patients should be called back to the site for follow-up immunogenicity assessment(s). Samples for immunogenicity should be collected every 12 weeks until the titer returns to baseline (ie, returns to within a single 2-fold dilution of the baseline titer) or until 1 year after the last dose of study treatment. A PK sample may be collected at the follow-up immunogenicity assessment(s) if warranted and agreed upon between both the investigator and sponsor. Every attempt should be made to contact patients for the follow-up immunogenicity assessment; however, if patients are unwilling or unable to return for the visit, this is not considered a protocol violation.

Instructions for the collection and handling of blood samples will be provided by the sponsor. The actual date and time (24-hour clock time) of each sampling will be recorded.

Immunogenicity will be assessed by a validated assay designed to detect antidrug antibodies (ADA) in the presence of glucagon at a laboratory approved by the sponsor. Antibodies may be further characterized and/or evaluated for their ability to neutralize the activity of glucagon.

Samples will be retained for a maximum of 15 years after the last patient visit, or for a shorter period if local regulations and ethical review boards (ERBs) allow, at a facility selected by the sponsor. The duration allows the sponsor to respond to future regulatory requests related to LY900018. Any samples remaining after 15 years will be destroyed.

9.8. Genetics

A blood sample will be collected for pharmacogenetic analysis as specified in the Schedule of Activities (Section 2), where local regulations allow.

Samples will not be used to conduct unspecified disease or population genetic research either now or in the future. Samples will be used to investigate variable exposure or response to nasal glucagon (LY900018) and to investigate genetic variants thought to play a role in diabetes mellitus and related complications. Assessment of variable response may include evaluation of AEs or differences in efficacy.

All samples will be coded with the patient number. These samples and any data generated can be linked back to the patient only by the investigative site personnel.

Samples will be retained for a maximum of 15 years after the last patient visit, or for a shorter period if local regulations and/or ERBs impose shorter time limits, for the study at a facility selected by Lilly or its designee. This retention period enables use of new technologies, response to regulatory questions, and investigation of variable response that may not be observed until later in the development of LY900018 or after LY900018 is commercially available.

Molecular technologies are expected to improve during the 15-year storage period and therefore cannot be specifically named. However, existing approaches include whole genome or exome sequencing, genome wide association studies, multiplex assays, and candidate gene studies. Regardless of technology utilized, data generated will be used only for the specific research scope described in this section.

9.9. Biomarkers

Not applicable.

9.10. Health Economics

Not applicable.

10. Statistical Considerations and Data Analysis

10.1. Sample Size Determination

Seventy five patients may be enrolled in order to have at least 66 patients (at least 30 patients with T1DM and T2DM, respectively) complete the study. For purposes of this study, a completer is defined as a patient who completes both periods with evaluable primary outcome. If patients discontinue from the study before completion of both periods with evaluable primary outcome for any reason, the patient may be replaced to ensure 66 patients complete the study. The replacement patients will be assigned the same treatment sequence as the patients to be replaced and will complete that treatment sequence in its entirety. Replacement should not occur beyond 75 patients enrolled, if it is expected to have at least 66 patients complete the study.

Assuming a non-inferiority margin (NIM) of 10%, a 98% treatment success rate for both treatment groups, and a within-patient correlation of zero, 66 completers will provide at least 90% power to show non-inferiority between LY900018 and IMG in treatment success from insulin-induced hypoglycemia with one-sided alpha level of 0.025 based on the Chi-square test.

The proposed NIM of 10% has been chosen based on the previously completed Phase 3 study (Rickels et al. 2016).

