LY900018: Single 3-mg dose; nasal administration by study site personnel IMG (GlucaGen, Novo Nordisk A/S): Single 1-mg dose; IM injection by study site personnel Patients will undergo a screening examination within 28 days prior to enrollment. Patients will be administered a single dose in Periods 1 and 2, which will be separated by a washout period of 3 to 14 days. Patients will return for a follow-up visit 26 to 30 days after the last study treatment.

Number of Patients:

Seventy five patients may be enrolled in order to have at least 66 patients (at least 30 patients with T1DM and T2DM, respectively) complete both periods with evaluable primary outcome. If patients discontinue from the study before completion of both periods with evaluable primary outcome for any reason, the patient may be replaced. Replacement should not occur beyond 75 patients enrolled, if it is expected to have at least 66 patients complete the study.

Statistical Analysis:

A total of 66 completers are required in the study in order to achieve the primary objective with at least 90% power using the following assumptions:

- A treatment success rate of 98% for both treatments
- A non-inferiority margin (NIM) of 10%
- One-sided alpha level of 0.025
- A within-patient correlation of zero between 2 treatment visits

The primary analysis will be a treatment comparison of the percentage of patients, including both T1DM and T2DM, who achieve treatment success. The percentage of patients who achieve treatment success within each treatment group and the difference in the percentages between the 2 treatment groups will be computed. A 2-sided 95% confidence interval (CI) will be obtained from the 1-sample mean of the paired differences in primary outcome (1=outcome observed; 0=outcome not observed) across 2 treatment visits. Non-inferiority of LY900018 will be declared if the upper limit of the 2-sided 95% CI constructed on the difference in percentage (IMG - LY900018) is less than the NIM of 10%.

2. Schedule of Activities

Study Schedule Protocol I8R-JE-IGBJ

Study Schedule Protoco	Screening		Period 1	Wash out		Period 2	Follow-up/ED	Additional Follow-up for TE ADA ^a	Comments
Procedure	Days -28 to -2	Day -1	Day 1	3 to 14 days	Day -1	Day 1	Within 28±2 days after last study treatment		
Clinical Assessments									
Informed Consent	X								
Randomization			X						
Admission to CRU		X			X				Admission can be rescheduled if PG level is not 90 to 250 mg/dL on Day 1.

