9.3 Efficacy Assessment

9.3.1 Primary Efficacy Analysis

The primary outcome is the treatment success, which is defined as an increase in plasma glucose (PG) to \geq 70 mg/dL or an increase of \geq 20 mg/dL from PG nadir within 30 minutes after receiving glucagon, without receiving additional actions to increase the PG concentration. The nadir is defined as the minimum PG concentration at the time of or within 10 minutes following glucagon administration.

The primary analysis will be a treatment group comparison of the primary outcome in the EAS. The percentage of patients achieving treatment success in each treatment group and the difference in percentages will be computed. A 2-sided 95% CI will be obtained from the 1-sample mean of the paired differences in primary outcome (1 = outcome observed; 0 = outcome not observed) across 2 treatment visits. Noninferiority of nasal glucagon (NG) will be declared if the upper limit of a 2-sided 95% CI constructed on the difference in percentages (IMG minus NG) is less than the noninferiority margin of 10%. Specifically, for each patient, the paired difference of treatment success between IMG and NG will be calculated and PROC TTEST will be used to create the 95% CI of the mean difference.

Primary efficacy analysis will only include patients who complete both treatment visits with evaluable primary outcome. The analysis will be performed separately for each diabetes type. The following will be considered as nonevaluable primary efficacy outcome and excluded from the analysis related to primary efficacy outcome:

Final, 01 Feb 2018 Page 10 of 26

- Patients with at least 1 treatment visit in which the nadir PG is \geq 70 mg/dL;
- Patients receiving an external measure to raise PG concentration either before glucagon administration or within the first 10 minutes after glucagon administration.

Plasma glucose concentrations assessed through a central laboratory will be used to assess treatment success.

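### At 66 completers the planned paired t interval meets the 90% power claim but not the stated one-sided 0.025: its exact error is about 5% to 9% at IMG success rates of 98% to 100%

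*Protocol*

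**What the plan says.** Protocol Section 10.1 makes one joint statement, repeated in SAP Section 7. It takes a 10% margin, 98% success on each treatment and no correlation between a patient's two visits. On that footing it claims that "66 completers will provide at least 90% power to show non-inferiority between LY900018 and IMG in treatment success". The same sentence then gives the error level and the test: "with one-sided alpha level of 0.025 based on the Chi-square test". The version of the chi-square test is not named. The protocol synopsis, under Statistical Analysis, is firmer: "A total of 66 completers are required in the study in order to achieve the primary objective with at least 90% power".

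The analysis is described elsewhere. Protocol Section 10.3.1.1 takes a two-sided 95% interval from the one-sample mean of the paired 0/1 differences. It declares non-inferiority if the upper limit for IMG minus LY900018 is below 10%. SAP Section 9.3.1 fixes the procedure: "PROC TTEST will be used to create the 95% CI of the mean difference". Up to 75 patients may be enrolled.

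**The concern.** The sample size is justified with one test and the trial is judged with another. With success near 98%, 66 patients yield only a handful of discordant pairs (patients who succeed on one treatment only). A t interval on paired 0/1 differences then takes its standard error from those few pairs, and with few or none of them it is too narrow. That raises power and false-positive risk together.

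This is the trial's only confirmatory test. A reader of Section 10.1 would believe that a nasal product truly 10 percentage points worse has a 2.5% chance of being declared non-inferior.

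**Working it through.** **Inputs.** n = 66; margin m = 0.10; success 0.98 on both treatments; correlation zero; one-sided 0.025 (Protocol 10.1, SAP 7). Decision rule from Protocol 10.3.1.1 and SAP 9.3.1. Let b be the number of patients who succeed on IMG only and c the number who succeed on LY900018 only.

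**1. The plan's power figure.** With zero correlation the paired difference has variance 2 × 0.98 × 0.02 = 0.0392.
- Unpooled normal formula: n = (1.960 + 1.2816)² × 0.0392 / 0.10² = 41.2, so 42.
- At n = 66: SE = √(0.0392/66) = 0.02437, and power = Φ(0.10/0.02437 − 1.960) = Φ(2.143) = 98.4%.

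The lower bound of 90% is met.

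**2. Exact power of the planned interval.** The upper limit is U = (b − c)/n + t × s/√n, with t = 1.997 on 65 df and s² = [(b + c) − (b − c)²/n]/(n − 1). Under the design assumptions P(IMG only) = P(LY only) = 0.98 × 0.02 = 0.0196. Summing multinomial probabilities over all (b, c) with U < 0.10 gives 96.3% at n = 66 and 97.4% at n = 75.

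**3. Exact one-sided error of the planned interval.** On the boundary, the LY900018 rate is the IMG rate minus 0.10. With zero correlation P(IMG only) = p_I(1 − p_L) and P(LY only) = (1 − p_I)p_L. The same enumeration gives:

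| True IMG / LY900018 | P(IMG only) | P(LY only) | Paired t error, n = 66 | Tango error, n = 66 |
|---|---|---|---|---|
| 98% / 88% | 0.1176 | 0.0176 | 4.9% | 1.6% |
| 99% / 89% | 0.1089 | 0.0089 | 6.4% | 1.3% |
| 100% / 90% | 0.1000 | 0 | 9.3% | 0.8% |

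At 75 completers the paired t errors are 4.6%, 5.5% and 5.0%.

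*Hand check of the last row.* If IMG never fails, c = 0 and b is Binomial(66, 0.10).
- b = 3: mean 0.0455, s = 0.2099, U = 0.0455 + 1.997 × 0.2099/8.124 = 0.097, which passes.
- b = 4: U = 0.120, which fails.
- Error = P(b ≤ 3) = 0.0010 + 0.0070 + 0.0253 + 0.0599 = 0.093.

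**4. A paired score interval for comparison.** Tango's statistic is z = (b − c − nm)/√[n(2q + m − m²)], where q is the estimate of P(LY only) restricted to the margin. Non-inferiority requires z < −1.960. When c = 0 and b ≤ 3, q = 0 and the denominator is √(66 × 0.09) = 2.437.
- b = 1: (1 − 6.6)/2.437 = −2.30, which passes.
- b = 2: −1.89, which fails.
- b = 3: −1.48, which fails.
- Error at 100% / 90% = P(b ≤ 1) = 0.0010 + 0.0070 = 0.8%.

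Exact power under the design assumptions is 81.1% at n = 66 and 87.7% at n = 75.

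**5. Whether 66 is a minimum.** For 90% power the unpooled formula needs 42, a continuity-corrected version about 60, and the Farrington-Manning score version 81. The planned interval has at least 90% exact power at every n from 49 to 89, the largest checked. No version tried gives 66 as the smallest n.

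**6. No discordant pairs.** Under the design assumptions this has probability (1 − 0.0392)^66 = 7.1%. The differences then have zero variance and the t interval collapses to a point at zero.

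**The case against.** The strongest reply is that the power claim is a lower bound and it is true, both by the usual formula (98.4%) and for the analysis that will be run (96.3%). A minimum n of 42 supports at least 90% at 66. All of that stands. A reader might infer that the power figure cannot be reproduced, or that the sample size must be either 42 or 81. The documents support neither: the chi-square version is unnamed, and a continuity-corrected version falls between the two.

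A reader might also infer that the trial's real power is about 80%. That figure belongs to score tests that neither document plans. Nor is it the power at exactly 2.5% error. Relaxing Tango's cut-off until its error at 98% / 88% is about 2.5% gives 89.7% power, but the error then reaches 3.3% at 100% / 90%. The 81% is the price of staying below 2.5% at all three rates. Similarly, the continuity-corrected test has 2.3% error at 98% / 88% and 89.5% exact power at 66, but 3.3% error at 100% / 90%.

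Subtracting the trials with no discordant pair would leave 96.3% − 7.1% = 89.2%. That is not a power shortfall. A zero-width interval at zero satisfies the written rule, and the score test passes such a trial too (z = −2.71).

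Finally, 0.025 can be read as a nominal level, which approximate methods seldom hit exactly. That is fair for small departures. Here the error is roughly two to four times nominal, at the control rates the plan expects: it assumes 98%, and Protocol Section 3.2 reports 75 of 75 IMG successes in the earlier study.

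**Conclusion.** The joint statement of sample size, power and alpha is not delivered by the planned analysis. The power part holds (96.3% exact at 66). The alpha part does not: the one-sided error at 66 completers is 4.9% to 9.3% for IMG rates of 98% to 100%, and 4.6% to 5.5% at 75 completers.

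Two lesser points follow. The sizing test differs from the analysis test. The synopsis's description of 66 completers as required is unsupported, since 66 was not the minimum under any version tried.

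The figures rest on the plan's zero within-patient correlation, carried over to the non-inferiority boundary, and on literal use of the decision rule. The error depends on the true IMG rate and is nearer nominal at lower rates (3.5% at 95% against 85%).

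**What to change.** Choose one of two courses and apply it consistently.

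1. Replace the paired t interval in Protocol 10.3.1.1 and SAP 9.3.1 with a Tango paired score interval. Restate power in the synopsis, Protocol 10.1 and SAP 7 as about 81% at 66 completers and about 88% at 75. This also removes the zero-width interval when no pair is discordant.
2. Keep the paired t interval. In the synopsis, Protocol 10.1 and SAP 7, state its exact power (about 96%) and its true one-sided error at 66 completers (about 5% to 9% at IMG rates of 98% to 100%). Say how a trial with no discordant pairs is judged.

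In either case, base the sizing statement on the interval used for the analysis, show how 66 was reached, and drop the claim that 66 is required.

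No patients are added. The cost is a less favourable stated figure: lower power in the first course, a higher admitted error in the second. The first course is also stricter. Two IMG-only successes and no LY900018-only success among 66 pass under the t interval (upper limit 7.3%) but not under the score interval.

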10.2. Populations for Analyses

10.2.1. Study Participant Disposition

A detailed description of patient disposition will be provided at the end of the study.

Proportion of patients discontinued from the study and the reasons for discontinuation will be summarized by treatment group for all randomized patients.

10.2.2. Study Participant Characteristics

The patients' baseline characteristics and demographic characteristics will be recorded, listed, and will be summarized for all randomized patients.

10.2.3. Treatment Compliance

No specific study data will be collected for analysis of treatment compliance.

10.3. Statistical Analyses

Statistical analysis of this study will be the responsibility of Eli Lilly and Company or its designee.

Efficacy, PK, and PD analyses will be conducted on the full analysis set. This set includes all data from all randomized patients receiving at least one dose of the investigational product according to the treatment allocation. Safety analyses will be conducted for all enrolled patients, whether or not they completed all protocol requirements. If a patient receives a glucose infusion to prevent the progression to severe hypoglycemia (see Section 9.2.4), data after IV glucose

infusion may be excluded from the efficacy and PD analyses. Details will be described in the statistical analysis plan (SAP).

Any change to the data analysis methods described in the protocol will require an amendment ONLY if it changes a principal feature of the protocol. Any other change to the data analysis methods described in the protocol, and the justification for making the change, will be described in the SAP and/or in the clinical study report.

Additional exploratory analyses of the data will be conducted as deemed appropriate. Study results may be pooled with the results of other studies for population PK analysis purposes to avoid issues with post-hoc analyses and incomplete disclosures of analyses.

10.3.1. Efficacy Analyses

10.3.1.1. Primary Efficacy Analysis

The primary objective is to demonstrate that 3 mg LY900018 is non-inferior to 1 mg IMG for the proportion (NIM=10%) of Japanese patients with T1DM or T2DM who achieve treatment success without receiving additional actions to increase the PG concentration. Treatment success is defined as either an increase in PG to \geq 70 mg/dL or an increase of \geq 20 mg/dL from PG nadir within 30 minutes after receiving study treatment. The nadir is defined as the minimum PG concentration at the time of or within 10 minutes following glucagon administration.

The primary analysis will be a treatment group comparison of the primary outcome. The percentage of treatment successes in each treatment group and the difference in percentages will be computed. A 2-sided 95% confidence interval (CI) will be obtained from the 1-sample mean of the paired differences in primary outcome (1=outcome observed; 0=outcome not observed) across 2 treatment visits. Non-inferiority of LY900018 will be declared if the upper limit of a 2-sided 95% CI constructed on the difference in percentages (IMG - LY900018) is less than the NIM of 10%.

Primary efficacy analysis will only include patients who complete both treatment visits with evaluable primary outcome. The following will be considered as non-evaluable primary efficacy outcomes and will be excluded from the analysis related to primary efficacy outcome:

- Patients with at least 1 treatment visit in which the lowest PG concentration at the time of or within 10 minutes following glucagon administration is ≥70 mg/dL;
- Patients who receive an external measure to raise PG concentration either before glucagon administration or within the first 10 minutes of glucagon administration.

Plasma glucose concentrations assessed through a central laboratory will be used to assess treatment success. Additional analysis will be performed if deemed necessary. The details will be provided in the SAP.

